5.7 Treatment after the end of the study

Not applicable - please see Section 4.1 for details of treatment after the study database has been closed.

6. DISCONTINUATION OF TREATMENT AND PATIENT WITHDRAWAL

6.1 Discontinuation of study treatment

Patients may be discontinued from investigational product (IP) in the following situations. Note that discontinuation from study treatment is NOT the same thing as a complete withdrawal from the study

- Patient decision. The patient is at any time free to discontinue treatment, without prejudice to further treatment
- Adverse Event
- Severe non-compliance with the Clinical Study Protocol
- Bone marrow findings consistent with myelodysplastic syndrome (MDS)/acute myeloid leukaemia (AML)

6.1.1 Procedures for discontinuation of study treatment

The investigator should instruct the patient to contact the site before or at the time if Study treatment is stopped. A patient that decides to discontinue Study treatment will always be asked about the reason(s) and the presence of any AEs. The date of last intake of Study treatment should be documented in the CRF (electronic or paper). All Study treatment should be returned by the patient at their next on-site study visit or unscheduled visit. Patients permanently discontinuing Study treatment should be given locally available standard of care therapy, at the discretion of the Investigator.

Any patient discontinuing investigational product should be seen post discontinuation for the evaluations and sample collections outlined in the study schedule.

After discontinuation of the study medication at any point in the study, all ongoing AEs or SAEs must be followed until resolution unless, in the Investigator's opinion the condition is unlikely to resolve due to the patients underlying disease, or the patient is lost to follow up (see Section 7.2).

Clinical Study Protocol - 6
Olaparib - ESR-18-13807

All new AEs and SAEs occurring during the 30 calendar days after the last dose of study medication must be reported (if SAEs, they must be reported within 24 hours as described in Section 8.4.1) and followed to resolution as above. Patients should be seen at least 30 days after discontinuing study medication to collect and / or complete AE information. For guidance on reporting adverse events after the 30 day follow up period see Section 7.3.2.1.

Discontinuation of Study treatment, for any reason, does not impact on the patient's participation in the study. The patient should continue attending subsequent study visits and data collection should continue according to the study protocol. If the patient does not agree to continue in-person study visits, a modified follow-up must be arranged to ensure the collection of endpoints and safety information. This could be a telephone contact with the patient, a contact with a relative or treating physician, or information from medical records. The approach taken should be recorded in the medical records. A patient that agrees to modified follow-up is not considered to have withdrawn consent or to have withdrawn from the study.

7. STUDY ASSESSMENTS AND PROCEDURES

7.1 Efficacy assessments

7.1.1 Clinical outcome assessments

Evaluate the percentage of patients who develop drug-induced folate deficiency while on olaparib, defined as serum folate level <7 ng/mL.

Determine the impact of folic acid supplementation on anemia, need for transfusion, and dose modification of olaparib as compared to those who did not receive/require folic acid supplementation.

Tumor assessment will be performed as per treating physician's decision and would include regular clinical exams, tumor marker monitoring, and imaging (body CT scans) at every 3 -6 month interval. Tumor response will be evaluated according to treating physician assessment. Response rate is defined as achievement of complete response (CR) or partial response (PR). Progression free survival, PFS, is defined as time from enrolment until disease progression or death. Patients who withdrew from olaparib before disease progression or death will be censored at the date of their last tumor assessment.

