of SSBs during DNA replication results in their conversion into the more serious DNA DSBs that would normally be repaired by HR repair. Olaparib has been shown to inhibit selected tumor cell lines in vitro and in xenograft and primary explant models as well as in genetic *BRCA* knock-out models, either as a stand-alone treatment or in combination with established chemotherapies.

Initially, olaparib has been FDA approved for the treatment of advanced ovarian cancer¹². Later, the indications have expanded. Currently, it is approved for the following indications¹³⁻¹⁶

- First-Line Maintenance *BRCAm* Advanced Ovarian Cancer (*gBRCAm* = germline *BRCA*-mutated or *sBRCAm* = somatic *BRCA*-mutated)

- First-Line Maintenance HRD-Positive Advanced Ovarian Cancer in Combination with Bevacizumab. Homologous recombination deficiency (HRD) positive status defined by either a deleterious or suspected deleterious *BRCA* mutation, and/or genomic instability.

- Maintenance Recurrent Ovarian Cancer in patients who are in complete or partial response to platinum-based chemotherapy.

- Advanced *gBRCAm* Ovarian Cancer in patients who have been treated with 3 or more prior lines of chemotherapy.

- gBRCAm*, HER2-Negative Metastatic Breast Cancer

- First-Line Maintenance *gBRCAm* Metastatic Pancreatic Cancer whose disease has not progressed on at least 16 weeks of a first-line platinum-based chemotherapy regimen

- HRR Gene-mutated Metastatic Castration-Resistant Prostate Cancer in patients with deleterious germline or somatic homologous recombination repair (HRR) gene-mutated metastatic castration-resistant prostate cancer (mCRPC) who have progressed following prior treatment with enzalutamide or abiraterone .

Molecular sequencing of the tumor DNA is increasingly used in clinical practice to identify molecularly-targeted agents that can potentially effectively and safely treat patients with advanced cancers. Olaparib is used in this setting when solid tumors harbor molecular alterations such as germline and somatic mutations in *BRCA1* and *BRCA2* genes, other genes in Homologous DNA Recombination pathway, etc¹⁷. A detailed description of the chemistry, pharmacology, efficacy, and safety of olaparib is provided in the package insert.

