7. Eastern Cooperative Oncology Group (ECOG) performance status 0-1).
8. Patients must have a life expectancy ≥ 16 weeks.
9. Patients with measurable and non-measurable disease are eligible.
10. There is no limit on the number of prior therapy lines. Olaparib can be used in the front or a subsequent lines of therapy as well as maintenance.
11. Patients can be enrolled with the lab results outside of the Inclusion criteria range or a performance status = 2, if olaparib is recommended by their treating oncologist/physician and the olaparib Package Insert is followed for dose adjustments.

Sex

12. Female or male

Clinical Study Protocol - 6
Olaparib - ESR-18-13807

Reproduction

13. Postmenopausal or evidence of non-childbearing status for women of childbearing potential: negative urine or serum pregnancy test within 28 days of study treatment and confirmed prior to treatment on day 1.

Postmenopausal is defined as:

- Amenorrheic for 1 year or more following cessation of exogenous hormonal treatments
 - Luteinizing hormone (LH) and Follicle stimulating hormone (FSH) levels in the post-menopausal range for women under 50
 - radiation-induced oophorectomy with last menses >1 year ago
 - chemotherapy-induced menopause with >1 year interval since last menses
 - surgical sterilisation (bilateral oophorectomy or hysterectomy)
14. Advise male patients with female partners of reproductive potential or who are pregnant to use effective contraception during treatment and for 3 months following the last dose of olaparib and to not donate sperm during this time.

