8.3 Populations for analyses

Clinical Study Protocol - 6
Olaparib - ESR-18-13807

All enrolled patients who receive at least one dose of olaparib will be included in the analysis population to be used to assess the efficacy and safety endpoints.

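### Response rate is taken over all dosed patients, with no response-assessable set and no rule for patients who enter with nothing to respond

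*Combined protocol and SAP*

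**What the plan says.** Section 7.1.1 defines the endpoint: "Response rate is defined as achievement of complete response (CR) or partial response (PR"). It adds: "Tumor response will be evaluated according to treating physician assessment". The tools are "regular clinical exams, tumor marker monitoring, and imaging (body CT scans) at every 3 -6 month interval". No response criteria are named, and no condition on baseline disease is attached.

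Section 8.3 sets the denominator: "All enrolled patients who receive at least one dose of olaparib will be included in the analysis population to be used to assess the efficacy". The same set serves for safety. No other population is defined.

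Eligibility is broad. Section 4.1 item 9 reads "Patients with measurable and non-measurable disease are eligible", and item 10 reads "Olaparib can be used in the front or a subsequent lines of therapy as well as maintenance". Four of the seven approved indications listed in the Introduction (after section 1.3) are maintenance indications. One of them is "Maintenance Recurrent Ovarian Cancer in patients who are in complete or partial response to platinum-based chemotherapy".

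The response rate is used in three ways:
- Section 8.4.1 compares it among randomised patients according to folic acid supplementation.
- Section 2 compares folate-deficient patients who receive folic acid with everyone who does not receive or need it.
- Both sections also set it against historical controls, which section 8.4.1 calls descriptive.

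The synopsis adds a hypothesis test for the group comparison. Section 8.4.1 reports results by cancer type, but not by measurable disease or maintenance setting. It leaves only the exploratory endpoint to the SAP.

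**The concern.** A patient who starts olaparib in complete response, or with no disease that can be assessed, has no route to a new CR or PR. Read together, sections 7.1.1 and 8.3 put that patient in the denominator. The reported rate then depends partly on how many such patients are enrolled, as well as on the activity of olaparib.

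This bears on the third hypothesis in section 8.1, that replacing folate leaves the antitumour effect of olaparib intact. Response rate is one of two endpoints that address it, the other being PFS. Patients who cannot respond in either group pull the absolute difference towards zero, which is the direction that would seem to support no effect. In the non-randomised comparison, a different patient mix can create a difference or hide one. Against published controls whose patients had assessable disease, the study rate would look low.

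**Working it through.** **The plan's own figure.** The only sample size is for folate deficiency: 66% against 50%, one-sided 0.05, 80% power, n=60. An exact binomial rule of at least 37 of 60 gives alpha 0.046 and power 0.802, and 60 / 0.8 = 75. The figure reproduces. It says nothing about response rate, for which the plan gives no expected rate, power or size.

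**Inputs.** The denominator, definition and eligibility come from the sections above. The non-assessable share f, the true response rates and the number randomised are not in the documents and are assumed below. About 25 per arm is a generous figure: 0.66 x 75 = 49.5 patients would be randomised if every expected folate-deficient patient qualified.

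**Step 1, overall rate.** If non-assessable patients are coded as non-responders, observed rate = true rate x (1 - f). For a true rate of 50%:
- f = 0.25: 37.5%
- f = 0.50: 25%
- f = 0.75: 12.5%

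The opposite coding is also open. If the 25% were all in CR at entry and that CR counted as achieved, the rate would be 0.5 x 0.75 + 0.25 = 62.5%.

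**Step 2, randomised comparison, equal f in both arms, coded as non-responders.** Both rates scale by (1 - f), so the difference does too and the ratio stays the same. With true rates of 60% and 40%, 25 per arm and two-sided 0.05:

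| f | Observed rates | Difference (points) | Ratio | Power, all patients | Power, assessable only |
|---|---|---|---|---|---|
| 0 | 60% v 40% | 20 | 1.5 | 29% | 29% |
| 0.2 | 48% v 32% | 16 | 1.5 | 21% | 24% |
| 0.4 | 36% v 24% | 12 | 1.5 | 15% | 19% |
| 0.6 | 24% v 16% | 8 | 1.5 | 10% | 14% |
| 0.8 | 12% v 8% | 4 | 1.5 | 7% | 9% |

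**Step 3, enrolment needed.** Two proportions, two-sided 0.05, 80% power: n per arm = [1.96 x sqrt(2 x pbar x (1 - pbar)) + 0.84 x sqrt(p1(1 - p1) + p2(1 - p2))]^2 / (p1 - p2)^2, where pbar is the mean of p1 and p2.
- 40% v 20%: 81.2 assessable patients per arm.
- f = 0.3, all patients, 28% v 14%: 131.7 enrolled. Assessable only: 81.2 / 0.7 = 116 enrolled.
- f = 0.5, all patients, 20% v 10%: 199.0 enrolled. Assessable only: 81.2 / 0.5 = about 162 enrolled.

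Like for like at f = 0.5, the cost is 199 / 162, or about 23% more patients.

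**Step 4, at about this trial's size.** With 25 per arm, f = 0.5 and true rates of 40% v 20%:
- All patients: z = 0.10 / sqrt((0.16 + 0.09) / 25) = 1.00, power about 17%.
- Assessable only (12.5 per arm): z = 0.20 / sqrt((0.24 + 0.16) / 12.5) = 1.12, power about 20%.

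**Step 5, non-randomised comparison, unequal f.** With a true rate of 50% in both groups and shares of 30% and 50%: 0.5 x 0.7 = 35% and 0.5 x 0.5 = 25%. This is a false 10-point difference, and swapping the shares reverses its sign.

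**The case against.** Three stronger readings are tempting, and the documents do not support them.

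- **No maintenance or non-measurable-disease patient can respond.** Section 7.1.1 rests on physician judgement with examination and tumour markers as well as imaging. A physician may record a response in non-measurable disease, and a maintenance patient entering in PR may improve. Only patients already in CR, or with no assessable disease, clearly cannot achieve a new response.
- **The plan counts these patients as non-responders.** Section 8.3 puts them in the population, but no section says how they are coded. Section 7.1.1 does not say whether a CR carried over from earlier therapy counts as achieved. If it does, the rate is inflated. The downward bias is therefore conditional on the coding.
- **The required size rises from 81 to 199 per arm.** That sets assessable patients against enrolled ones. The like-for-like contrast is about 162 against 199.

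The other side also has a fair point on the randomised comparison in section 8.4.1. There the non-assessable share is balanced in expectation, so no systematic false difference arises and the ratio is preserved. The mix bias belongs to the section 2 comparison. Reporting by cancer type may separate some of the mix, though not by disease status at entry. The historical comparison is only descriptive, the study is a pilot, and the test has little power under either denominator.

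These points narrow the concern but do not remove it. Whichever comparator is used, the denominator is not limited to patients who could respond, and their coding is left open.

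**Conclusion.** The point holds in a limited form. As written, the response-rate denominator includes any dosed patient who enters in CR or without assessable disease, and the coding of those patients is unspecified.

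If they are coded as non-responders:
- The overall rate and the randomised absolute difference fall by the factor (1 - f), and the ratio is unchanged when f is equal.
- The historical comparison is biased down where the controls had assessable disease.
- The section 2 comparison can be biased either way, by 10 points in the example.

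All sizes rest on assumed shares and rates, because the documents give neither. The gain in power from restricting the set is small (z 1.12 against 1.00 at 25 per arm). The main benefit is a response rate that can be interpreted and a coding rule fixed before the data are seen. This should be changed, but it concerns a secondary endpoint. The primary endpoint and N=75 are unaffected.

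**What to change.** In sections 8.3 and 8.4.1:
- Define a response-assessable set: dosed patients with disease assessable at baseline by the treating physician and not in CR at entry, recorded before the first olaparib dose. That record precedes randomisation, so restricting to the set does not break the randomised comparison. Requiring measurable disease would be narrower than needed, since section 7.1.1 lets physicians judge response by other means.
- Use this set for every response-rate estimate and comparison, and report the number in each group.
- Keep all dosed patients for PFS.
- Show the response rate in all dosed patients as a sensitivity analysis, and state how patients outside the set are coded there.
- Reconcile the comparator groups in sections 2 and 8.4.1, and label any comparison beyond the randomised patients as non-randomised.

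The cost is some wording, one baseline field and fewer patients in the main response-rate analysis.

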1.4 Study rationale

See Section 1.2.

We have observed folate deficiency in 66% of patients of patients with advanced ovarian and metastatic breast cancer occurring within weeks of treatment initiation with olaparib^{2, 3}. While folate deficiency is a known cause of macrocytic anemia, it has not been previously reported in association with olaparib therapy. Since macrocytic anemia is a known complication of olaparib treatment regardless of the cancer type treated, folate deficiency can occur in these patients too.

Clinical Study Protocol - 6
Olaparib - ESR-18-13807

This study is conducted to assess the prevalence and timing of folate deficiency in patients with ovarian, breast, pancreatic, prostate, and other cancers that may benefit from olaparib as determined by their treating physicians based on their tumor sequencing or germline results. .

As folic acid supplementation has not been studied prospectively in this patient population, this study will also evaluate, in a randomized fashion, the impact of folic acid supplementation on anemia and need for transfusion as compared to a placebo group (i.e. no folic acid supplementation while on olaparib).

Background

Olaparib is generally well tolerated. For instance, in the clinical trial of maintenance olaparib monotherapy in patients with platinum-sensitive ovarian cancer who had had 2 or more lines of platinum-based chemotherapy (Study 19), adverse reactions led to olaparib dose interruption, reduction and discontinuation in 35 %, 26 %, and 6 % of patients, respectively¹³. Olaparib is known to cause hematologic toxicity. In the pooled analysis of multiple clinical trials, the following hematologic side effects were observed: anemia in 37% of patients, Macrocytosis (elevated mean corpuscular volume) is reported in up to 89% of patients treated with olaparib¹³. The manufacturer recommends monitoring blood counts at baseline and monthly thereafter, interrupting treatment until any hematologic toxicity has resolved to \leq grade 1, with additional evaluation if blood counts do not recover after 4 weeks of treatment interruption, including bone marrow and cytogenetic analyses^{5, 6}. Little is known about the etiology of olaparib-induced hematologic toxicity.

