2. OBJECTIVES AND ENDPOINTS

Primary objective:

To determine the frequency and timing of folate deficiency in patients with solid tumors harboring molecular alterations such as germline and somatic mutations in *BRCA1* and *BRCA2* genes, other genes in Homologous DNA Recombination Repair (HRR) pathway, genomic stability as determined by Homologous Recombination Deficiency (HRD) assay, etc., who are treated with olaparib.

Secondary objectives:

To evaluate the effect of folic acid supplementation on serum folate, hemoglobin level, transfusion needs/number of transfusions, and need for olaparib treatment interruption, dose reduction and drug discontinuation.

To assess response rate (RR) to olaparib as it relates to serum folate level and folic acid supplementation.

Clinical Study Protocol - 6
Olaparib - ESR-18-13807

To assess progression-free survival (PFS) as it relates to serum folate level and folic acid supplementation.

Exploratory objectives:

To elucidate the mechanism of folate deficiency in patients treated with olaparib including possible interaction with germline *BRCA1* and *BRCA2* mutations via testing for folate receptors using immunohistochemistry on available paraffin embedded tumor samples from enrolled patients.

Primary endpoint:

The primary binary endpoint of the study is the percentage of patients who develop drug-induced folate deficiency, defined as serum folate level <7 ng/mL, within three months from start of olaparib therapy.

Secondary endpoints:

To assess the impact of folic acid supplementation on anemia, need for transfusion, and olaparib treatment interruption, dose reduction and drug discontinuation as compared to those who did not receive/require folic acid supplementation

To determine tumor response rate (RR), using treating physician assessment, on olaparib therapy in patients who develop folate deficiency and receive folic acid supplementation as compared to those who do not receive/require folic acid supplementation. Will also compare RR to historical controls (patients with solid tumors treated with olaparib or other approved agents on clinical trials).

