To determine progression-free survival (PFS), using treating physician assessment based on olaparib therapy in patients who develop folate deficiency and receive folic acid supplementation as compared to those who do not receive/require folic acid supplementation. Will also compare PFS to historical controls (patients with solid tumors treated with olaparib or other approved agents on clinical trials) using published data.

Exploratory Endpoints:

To evaluate association between:

- *BRCA 1*, *BRCA 2*, and other HRR gene status (germline mutation carrier vs non-carrier) and the intensity of folate receptor alpha expression in the tumor ($<50\%$ or $>50\%$)
- *BRCA 1*, *BRCA 2*, and other HRR gene status (germline mutation carrier vs non-carrier) and nadir serum folate level during olaparib treatment

Clinical Study Protocol - 6
Olaparib - ESR-18-13807

- *BRCA 1*, *BRCA 2*, and other HRR gene status (germline mutation carrier vs non-carrier) and tumor response in patients receiving folate supplementation as compared to patients not receiving folate supplementation and historical controls
- Folate deficiency and expression of folate receptors in patients' tumor samples

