4.2 Exclusion criteria

Medical conditions

1. Patients with folic acid deficiency, defined as folate <7 ng/mL, or those taking folic acid supplementation within 30 days of olaparib initiation.
2. Other malignancy unless curatively treated with no evidence of disease for ≥ 5 years except: adequately treated non-melanoma skin cancer, curatively treated in situ cancer of the cervix, ductal carcinoma in situ (DCIS), Stage 1, grade 1 endometrial carcinoma. Patients with a history of localised triple negative breast cancer may be eligible, provided they completed their adjuvant chemotherapy more than three years prior to registration, and that the patient remains free of recurrent or metastatic disease
3. Persistent toxicities (>Common Terminology Criteria for Adverse Event (CTCAE) grade 2) caused by previous cancer therapy, excluding alopecia.
4. Patients with myelodysplastic syndrome/acute myeloid leukaemia or with features suggestive of MDS/AML.

Clinical Study Protocol - 6
Olaparib - ESR-18-13807

5. Patients with symptomatic uncontrolled brain metastases. A scan to confirm the absence of brain metastases is not required. The patient can receive a stable dose of corticosteroids before and during the study as long as these were started at least 4 weeks prior to treatment. Patients with spinal cord compression unless considered to have received definitive treatment for this and evidence of clinically stable disease for 28 days.
6. Patients considered a poor medical risk due to a serious, uncontrolled medical disorder, non-malignant systemic disease or active, uncontrolled infection. Examples include, but are not limited to, uncontrolled ventricular arrhythmia, recent (within 3 months) myocardial infarction, uncontrolled major seizure disorder, unstable spinal cord compression, superior vena cava syndrome, extensive interstitial bilateral lung disease on High Resolution Computed Tomography (HRCT) scan or any psychiatric disorder that prohibits obtaining informed consent.
7. Patients unable to swallow orally administered medication and patients with gastrointestinal disorders likely to interfere with absorption of the study medication.
8. Immunocompromised patients, e.g., patients who are known to be serologically positive for human immunodeficiency virus (HIV).
9. Patients with known active hepatitis (i.e. Hepatitis B or C).

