8.4 Statistical analyses

8.4.1 Efficacy analyses

Patients will be monitored for development of anemia and folate deficiency at scheduled time points throughout the course of the study, as described in Section 1.1. Patients who develop \leq G2 cytopenias and folate deficiency will be randomly assigned in a 1:1 ratio to receive folic acid supplementation 1 mg daily or no supplementation. Patients who develop G3 or higher cytopenias and folate deficiency will be started on folic acid supplementation, thus not included in the randomization. For patients who are randomized, we will assess the impact of folic acid supplementation on anemia, need for transfusion, and dose interruption, dose reduction and drug discontinuation of olaparib as compared to those who did not receive/require folic acid supplementation. Additionally, PFS and RR to olaparib will be compared amongst randomized patients relative to folic acid supplementation.

The statistical analysis will provide descriptive summaries as well as 95% confidence intervals for the primary endpoint of drug-induced folate deficiency in addition to response rate and other secondary endpoints. Kaplan-Meier methodology will be used to estimate the PFS curve and estimate of median PFS and corresponding 95% confidence interval will be provided. The significance of the observed percentage of folate-deficient cases will be assessed by statistical hypothesis test, as well as by multivariable analysis of the binary endpoint of folate deficiency adjusted by important covariates. Covariates will include age, race/ethnic group, previous therapy, Hgb prior to olaparib therapy, genetic testing result (*BRCA* carrier status). RR and PFS will be compared to historical controls as a descriptive comparison. Analyses will be reported on the entire combined cohort of patients with solid tumors and also separately for each cancer type. The statistical analysis of the exploratory endpoint will be specified in the SAP. Statistical analysis will be performed in the R Statistical software. No adjustment for multiplicity will be made.

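### The all-patient PFS and RR comparison in Section 2 groups patients by folic acid started weeks to months after the PFS clock begins, which builds in immortal-time bias that tends to favour folic acid

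*Combined protocol and SAP*

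**What the plan says.** Section 7.1.1 sets one time origin for everyone: "Progression free survival, PFS, is defined as time from enrolment until disease progression or death".

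Section 2 defines the secondary PFS endpoint as a comparison "in patients who develop folate deficiency and receive folic acid supplementation as compared to those who do not receive/require folic acid supplementation". RR is split in the same way, and the Synopsis (1.2) plans a hypothesis test of RR between the supplemented group and its comparator. Section 8.3 puts every patient who takes at least one olaparib dose in the analysis population.

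Nobody should be in the supplemented group at time zero, because Section 4.2 excludes "Patients with folic acid deficiency, defined as folate <7 ng/mL, or those taking folic acid supplementation within 30 days of olaparib initiation". (Section 5.5 lets patients who decline to stop folate-containing vitamins take part.) Deficiency is expected later: "occurring within weeks of treatment initiation with olaparib" in Section 1.4, and the primary endpoint counts it "within three months from start of olaparib therapy". Section 1.1 item 5 adds a confirmatory draw 2 weeks after the first low value, before any randomisation.

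Section 8.4.1 has patients with deficiency and cytopenia "randomly assigned in a 1:1 ratio to receive folic acid supplementation 1 mg daily or no supplementation", and says: "Additionally, PFS and RR to olaparib will be compared amongst randomized patients relative to folic acid supplementation". For PFS it names only Kaplan-Meier estimation. Under Section 3.1, randomised patients whose haemoglobin falls below 10 g/dl with deficiency receive folic acid whatever their arm. The documents do not say whether they are then analysed as randomised or as treated.

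**The concern.** To enter the supplemented group, a patient must stay progression-free and on study long enough to become deficient, be confirmed and start folic acid. The time before that start is event-free by construction, yet it is credited to folic acid. Patients who progress first all fall on the other side. RR has the same fault: early progressors are non-responders who can only be unsupplemented, and a response that precedes folic acid counts in its favour.

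The third hypothesis in Section 8.1 is that folate replacement leaves olaparib's antitumour effect intact. A comparison that leans towards folic acid is a poor test of that, because it could mask a harm.

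**Working it through.** **The plan's own figure.** The documents give no sample size, event count or power for PFS. The primary-endpoint size reproduces (exact binomial, n = 60, reject at 37 or more: one-sided alpha 0.046, power 0.802; 60/0.80 = 75) and is not in dispute. It matters here only because it fixes N = 75.

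**Inputs from the documents.** 66% become deficient (8.2); onset between weeks and 3 months (1.4, 2), taken as uniform over 0.5–3 months; 0.5 month for confirmation (1.1 item 5); study end at 7 months (3.4); imaging every 3–6 months plus clinical examination and markers (7.1.1).

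**Assumptions not in the documents.** Exponential PFS with median 4–18 months; share of deficient patients supplemented 30%, 50% or 100%; 40% crossover in the placebo arm where needed. Folic acid has no effect on PFS (true HR 1.00).

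**Check by hand** (median 6 months, 50% supplemented, every start placed at its mean, 1.75 + 0.5 = 2.25 months):
- Hazard = ln 2/6 = 0.1155 per month. Share destined for folic acid = 0.66 × 0.50 = 0.33.
- Progression-free at 2.25 months: exp(−0.1155 × 2.25) = 0.771. At 7 months: 0.445.
- Supplemented group, per patient enrolled: events 0.33 × (0.771 − 0.445) = 0.1075. Time after start 0.1075/0.1155 = 0.930 months; time before start 0.33 × 2.25 × 0.771 = 0.573. Rate counted from enrolment = 0.1075/(0.930 + 0.573) = 0.0715.
- Everyone else: events 0.67 × (1 − 0.445) + 0.33 × (1 − 0.771) = 0.447. Total time 0.447/0.1155 = 3.870, less the 0.573 credited to the other group = 3.297. Rate = 0.447/3.297 = 0.1356.
- Apparent rate ratio = 0.0715/0.1356 = **0.53**, with no true effect.
- Moving the 0.573 months back to unsupplemented time gives 0.1075/0.930 = 0.1155 and 0.447/3.870 = 0.1155, a ratio of **1.00**. The whole distortion is that misassigned time.

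**Null simulation, Section 2 comparison, 7 months, progression dated when it occurs:**

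| Deficient patients supplemented | Apparent HR, median PFS 4–18 months |
|---|---|
| 30% | 0.54–0.62 |
| 50% | 0.51–0.58 |
| 100% | 0.37–0.41 |

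With N = 75 and 50% supplemented, a two-sided 5% log-rank test, if one were run, would falsely favour folic acid in 13% of trials (median 18 months) to 46% (median 4 months), against a nominal 2.5%.

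**Sensitivity (50% supplemented, 7 months, median 6 or 12):**
- Half of progressions dated only at 3-monthly scans: 0.68–0.70. All of them: 0.86 (0.85–0.89 across checks). All of them, with deficiency always starting by 1.5 months: 1.00.
- Deficiency arising over 0.5–6 months, progression dated when it occurs: 0.36–0.37.
- Supplemented-type patients at 1.5 times the hazard: 0.74–0.78 with exact dating, 1.26–1.28 with scan-only dating.
- Follow-up of 24 months, exact dating, no prognostic difference, 30–50% supplemented, median 4–18: 0.64–0.84.

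**Randomised set (8.4.1):** as randomised 0.96–1.02, even with PFS counted from enrolment. As treated, with 40% placebo crossover, 0.69–0.73 at 7 months.

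**After correction of the all-patient comparison:** folic acid as a time-dependent covariate 0.98–1.02; landmark at 3.5 months 0.96–1.03.

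The RR bias follows from the same structure; its size was not calculated.

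**The case against.** The best defence is that Section 8.4.1 already holds a sound comparison. A patient who progresses before randomisation is in neither arm, and time from enrolment to randomisation is balanced by 1:1 allocation. A reader might infer that the randomised PFS comparison is also biased and would hide harm; the documents do not support that. With a true post-randomisation HR of 1.5, a Cox model returned 1.51 and 1.53 (medians 6 and 12 months) from either time origin. Starting at enrolment there lengthens both medians, and counting responses that precede allocation dilutes an RR difference. Neither favours folic acid. Bias returns only if placebo patients who later receive folic acid are counted as supplemented, which the plan leaves open.

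It can also be said that 8.4.1 applies the receive/require wording to randomised patients, so Section 2 may have meant only them. That reading is possible, but Section 2 does not say so and Section 8.3 includes all dosed patients.

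Two further inferences go too far. An apparent HR of about 0.4 needs every deficient patient to be supplemented, against the 1:1 allocation. And an inflated comparison of the supplemented group with historical controls is not established: 8.4.1 calls the historical comparison descriptive, and the documents do not say that this subgroup is the one compared.

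Finally, this is a secondary endpoint in a pilot study, with no PFS test named. That lowers the priority; it does not repair the comparison.

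**Conclusion.** The point holds for the Section 2 all-patient comparison of PFS and RR. Groups are formed after time zero, and nothing in the plan corrects for it. Under no true effect the apparent HR is about 0.5–0.6 with 30–50% of deficient patients supplemented, 7 months of follow-up and progression dated when it occurs. Median PFS and the supplemented share are assumptions. The share cannot be derived from the documents, partly because Sections 1.1 and 8.4.1 describe different thresholds for supplementing without randomisation; those passages need reconciling.

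A benefit for folic acid is the expected direction, not a certainty. Scan-only dating brings the ratio to about 0.85–0.89, and a worse prognosis in anaemic, deficient patients could cancel or reverse it. The as-randomised comparison is sound and the primary endpoint is unaffected. The plan should be changed, but this need not hold up the trial.

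**What to change.** 1. In 8.4.1, name the as-randomised comparison as the PFS and RR analysis of folic acid. Time PFS from randomisation, count only CR or PR first documented after randomisation, and state that placebo patients who later receive folic acid stay in their assigned arm.
2. For the Section 2 all-patient comparison, enter deficiency and start of folic acid as time-dependent covariates. The alternative is a pre-specified landmark at about 3.5 months (the 3-month window plus confirmation), grouped by supplementation status at that date. Label it descriptive in either case: both remove the misassigned time, but not confounding by prognosis.
3. Keep PFS from enrolment for the whole-cohort Kaplan-Meier curve.

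The cost is wording. Folate tests are scheduled, folic acid and vitamin intake are recorded under 5.4 and 5.5, and randomisation is dated; the date of first documented response must be captured if the CRF does not already hold it. The landmark drops early progressors and leaves 7 − 3.5 = 3.5 months before study end, so the time-dependent analysis is preferable.
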